11.4. Data Storage

See Section 8.0.

11.5 Data Release

A well-documented and appropriately accessible archive of study data is an important resource that will result from this study. The research team recognizes the need to share final data from the study with the larger scientific community. The Asthma Action at Erie Trial recognizes the requirements of data sharing set forth by the NIH. Three years after the end of clinical activity or two years after the main paper of the trial has been published (whichever comes first), data will be publically released. Data sets from the Trial will be stripped of all protected personal health information (PHI) to allow sharing of data without compromising participant confidentiality, privacy, and safety. All identification covered under HIPAA will be removed. All remaining variables not covered under HIPAA will be evaluated in terms of the risk of deductive disclosure of identity, and appropriate measures will be taken to protect confidentiality. The striped data, in partnership with the community clinical partner, will be sent to the NIH Program Officer for public release. In order to ensure responsible usage of study data, user registration will be required in order to access or download data files. Registered users will receive technical assistance with

questions or problems from the Methodology Research Core at the University of Illinois at Chicago's Institute for Health Research and Policy. A data sharing agreement will be required that will describe the conditions and restrictions of their use; limited data access will be made available only to users who successfully complete a rigorous approval process by both the investigators and the community partners. Data sets will be encrypted for transfer to approved investigators.

12.0 Statistical Considerations

Statistical analysis is described in Section 9.0. The sample size for the study was determined to allow assessment of the relative efficacy of the proposed interventions with respect to asthma control. While a strong clinical definition of asthma control has been in place for some time, there is no gold standard for assessing asthma control. The Asthma Control Questionnaire (ACQ) has been validated in diverse, large samples but currently there is an absence of substantive data on this test (data such as variability and reasonable effect sizes within this target population) upon which statistical power and sample size estimates can be based. Therefore we have conducted two calculations to ensure adequate power. Using the ACQ, a sample size of 100 per group (total N=200) had power 0.87 to detect the minimally important difference (MID) of 0.5 established for this test.¹⁴ We performed a separate power calculation using number of days with activity limitation (over the past 14-days) as Zeiger et al.⁴² found "activity limitation" to be a strong determinant of the composite asthma control score. In a multi-site inner-city (including Chicago) randomized trial of a home CHW asthma intervention, Morgan et al. reported activity limitations over the previous 14 day period.⁴³ Based on their data, we hypothesize a mean of 3.9 "activity limitation" days at baseline in both groups (SE 0.22) and, in the AE-C comparison group, a mean at 12 months of 2.84 days (SE 0.10). We anticipate the proposed CHW intervention will be more potent than that tested by Morgan et al. because it involves a higher dose and more physician involvement. Within the proposed CHW home intervention group, we anticipate a mean of 2 "activity limitation" days over a 14-day period at 12 months (SE 0.10), representing a 30% reduction from the AE-C comparison group (and 50% reduction from the baseline mean). Further assuming an attrition rate of 15% and 80% power, the standard two-group t-test for comparing means (at 12 months) requires a sample size of about 111 per group, for a total of 223 participants. Analyses to examine heterogeneity of treatment effects by age, race, or other groups have more limited power but results will be considered suggestive for further research.

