3.0 Objectives/Aims

Primary Aim 1: To assess the efficacy of the integrated CHW home asthma intervention, relative to clinic-based AE-C education over 12-months, as demonstrated by asthma control. We hypothesize that the CHW arm will have significantly greater asthma control than the AE-C arm at 12-months as measured by days with activity limitation over the previous 14 days and the Asthma Control Test/childhood Asthma Control Test.

Specific Aim 2: To assess maintenance of intervention efficacy, as demonstrated by asthma control at 18 and 24 months after randomization. We hypothesize that changes in efficacy outcomes will be maintained after cessation of the intervention.

Specific Aim 3: To determine the cost-effectiveness at 12-months of CHW and AE-C intervention delivery, and additional costs or savings related to asthma exacerbations at 12- and 24-months.

Specific Aim 4: To assess the efficacy of the integrated CHW home asthma intervention relative to clinic-based AE-C education, as demonstrated by asthma control, among those experiencing depression, stress, and/or post-traumatic stress disorder (PTSD). We hypothesize that among those living with depression, stress, and/or PTSD, the CHW intervention will be significantly more effective in achieving and maintaining asthma control than the AE-C education intervention.

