Participants that fail the screener or who chose to not provide informed consent will be thanked for their time. Participants that fail the screener but are interested in the study will be offered the option of being put on a re-contact list. If they agree to be put on this list, their contact information will be saved and research staff can call them again in several months to rescreen them. Personal identifying data from the screening (initial and re-contact lists) will be kept in a secure location until recruitment is ended, at which point it will be destroyed. (We will keep their name during the recruitment period only to prevent contacting people who have screened out.) All staff involved in recruitment will receive careful training about the study and the clinic services to ensure that everyone approached understands that participation is voluntary and services at Erie will continue regardless of study participation, and so that Erie staff understands their primary role is patient care. Recruitment will not impinge on clinical responsibilities or clinic operations. Staff involved in recruitment have their time covered by the study. Providers who refer the study to patients do so when they have time and feel comfortable only.

Randomization will be conducted in a 1:1 ratio using randomly mixed permuted blocks of size 4 and 6 to ensure reasonably equal allocation while reducing predictability of the assignment sequence. Upon completion of the randomization assignment, the data management team will generate a letter to the participant informing him/her of their study status and also notify the Erie Intervention Coordinator who will assign the patient to a CHW if randomized to that arm. Although double blinding in a behavioral randomized clinical trial is impossible, blinding will be maximized by: 1) incomplete disclosure of study goals for participants during consent (see Human Subjects for details), 2) blinding outcomes assessors; 3) incomplete disclosure of research hypotheses for non-investigators staff; and 4) training co-investigators and staff in the concept of equipoise. Intervention investigators and staff will be unblinded to treatment arm because they will need to work with the CHWs and monitor intervention fidelity and data accuracy. Study staff and investigators (with the exception of the Safety Officer) will not have access to interim outcomes data.

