9.0 Data Analysis

All analyses will be performed by the investigators and analysts in the Institute for Health Research and Policy using SAS version 9.4. We will compare key population descriptors in the two treatment groups as patient recruitment progresses (at N=100 and N=150) to ensure that the randomization process is achieving reasonable balance, being careful to protect operational staff from bias. Basic summary statistics will be calculated for outcome variables and covariates. Continuous variables will be assessed for normality using Q-Q plots and compared using 2-sample t-tests. If distributions are sufficiently non-normal, then a suitable transformation or non-parametric test will be used. Categorical variables will be compared using chi-square tests. Significance tests will be two-sided at level $\alpha=0.05$.

Specific Aim 1: To assess the efficacy of the integrated CHW home asthma intervention relative to the AE-C intervention at 12-months post-randomization as demonstrated by asthma control. This study will employ two primary measures of asthma control: number of days with activity limitation over the previous 14 days and the Asthma Control Test/childhood Asthma Control Test (ACT/cACT). The mean total number of days with activity limitation over the previous 14-day period will be assessed at 12-months between the two treatment arms using the two-sample t-test or Mann-Whitney test. If the mean days with activity limitation in the intervention arm is at least 30% lower than that of the AE-C arm and $p < 0.05$, we will conclude that the CHW intervention is more effective. The ACT/cACT will be analyzed using similar methods; a MID of 0.2 will be used to determine intervention efficacy. Linear mixed models will

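### One of the two primary measures, ACT/cACT, has no power calculation; the questionnaire power of 0.87 in Section 12.0 is for the ACQ, which Section 9.0 does not analyse

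*Combined protocol and SAP*

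**What the plan says.** Section 3.0 frames the Aim 1 hypothesis at 12 months "as measured by days with activity limitation over the previous 14 days and the Asthma Control Test/childhood Asthma Control Test". Section 9.0 agrees: "This study will employ two primary measures of asthma control: number of days with activity limitation over the previous 14 days and the Asthma Control" Test in its adult and childhood forms. Section 9.0 also gives a threshold for judging efficacy on ACT/cACT, an MID of 0.2, with no unit, SD or source.

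Section 12.0 notes that data on ACQ variability and plausible effects in this population are lacking, and continues: "Therefore we have conducted two calculations to ensure adequate power". The first calculation is on the ACQ: "Using the ACQ, a sample size of 100 per group (total N=200) had power 0.87 to detect the minimally important difference" of 0.5. The second is on activity-limitation days: 2.84 against 2 days at 12 months, 80% power, 15% attrition, about 111 per group and 223 in total.

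Elsewhere in the current text the ACQ is one of the alternative entry criteria for uncontrolled asthma (Section 4.1) and a listed instrument (outcome table, Section 6.8). It is absent from Sections 3.0 and 9.0.

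**The concern.** The pair of measures in the power section is not the pair to be tested. The ACQ figure cannot stand in for ACT/cACT, because the protocol treats them as separate instruments:

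- They have separate rows in the outcome table, with 6 items against 5 to 7.
- Their entry cuts point in opposite directions: 1.25 or more on the ACQ, below 20 on ACT/cACT.
- Their stated MIDs differ: 0.5 against 0.2.

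No conversion between them is offered.

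At stake is how an ACT/cACT result will be read. Someone who sees 0.87 beside a questionnaire of asthma control may carry it over to the primary questionnaire. If ACT/cACT then shows no difference, no planned power exists to set the result against, and the one threshold the plan does give is small relative to what this sample can detect.

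**Working it through.** **1. The sections side by side.**

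| Measure | Sections 3.0 and 9.0 | Section 12.0 |
|---|---|---|
| Activity-limitation days | Primary | 80% power, 111 per group, N=223 |
| ACT/cACT | Primary, MID 0.2 | Nothing |
| ACQ | Absent | Power 0.87 at 100 per group, MID 0.5 |

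**2. The plan's 0.87.** Method: two-sample t-test, two-sided alpha 0.05 (Section 9.0), 1:1 allocation (Section 5.0). The noncentrality is d / (SD × √(2/n)). No ACQ SD is stated, so the figure cannot be reproduced independently and the SD has to be back-solved. With SD 1.14, the noncentrality is 0.5 / (1.14 × √(2/100)) = 3.10 on 198 degrees of freedom, and power is 0.87. Other SDs give 0.94 (SD 1.0), 0.83 (SD 1.2) and 0.77 (SD 1.3).

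**3. Which calculation sets N.** For days, d = 2.84 − 2 = 0.84. With n = 2 × (1.960 + 0.842)² × (SD/0.84)², an SD of 2.05 gives 93.5, rounded up to 94 per arm. Then 94 / 0.85 = 110.6, or 111 per arm. This matches the plan, although the SD of 2.05 is again back-solved; only standard errors are given. So the target of 223 comes from days. The ACQ line, at 100 per group, does not set it.

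**4. Completers.** 223 × 0.85 = 189.55, and 189.55 / 2 = 94.8, about 95 per arm. For the ACQ at 95 per arm and SD 1.14, the noncentrality is 0.5 / (1.14 × √(2/95)) = 3.02 and power is 0.85.

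**5. ACT/cACT at the plan's own 0.2.** With 95 per arm, √(2/95) = 0.145.

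- *If 0.2 means 0.2 SD:* the noncentrality is 0.2 / 0.145 = 1.38 and power is about 0.28. For 80% power, n = 2 × 2.802² / 0.2² = 392.4, so 393 evaluable per arm, or 393 / 0.85 = 462.4, so 463 enrolled per arm.
- *If 0.2 means raw points:* the SD is an assumption. Power below counts rejections in both tails.

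| Assumed SD (points) | Noncentrality | Power |
|---|---|---|
| 1 | 1.38 | 0.28 |
| 2 | 0.69 | 0.11 |
| 3 | 0.46 | 0.07 |
| 4 | 0.34 | 0.06 |
| 5 | 0.28 | 0.06 |

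**6. What 95 per arm can detect.** At 80% power the detectable difference is (1.960 + 0.842) × 0.145 = 0.41 SD. For assumed SDs of 3, 4 and 5 points that is about 1.2, 1.6 and 2.0 points.

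**The case against.** The strongest reply is that the enrolment target never depended on the ACQ. It rests on activity-limitation days, which is a primary measure and the only outcome in the abstract's hypothesis. Deleting the ACQ sentence would leave 223 unchanged. That is right, and it limits the point to one of the two primaries. A reader might infer that neither tested endpoint is powered, or that the trial was sized on the wrong questionnaire. The documents support neither reading.

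It can also be said that Section 12.0 speaks of asthma control in general, names the ACQ openly, and nowhere claims that 0.87 belongs to a primary measure. That is fair as to wording. It still leaves ACT/cACT without a stated basis in the only section that justifies the sample size.

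A third reply is that 0.2 is a threshold for judging efficacy, not the effect the trial expects, so the true difference could be larger. This stands too. A reader might infer that the trial is shown to be underpowered for ACT/cACT. It is not: with no SD and no expected effect, the documents show neither adequate nor inadequate power. The 0.28 is conditional on a true difference equal to the threshold.

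Finally, a null ACT/cACT result could still be read from its confidence interval. True, but that does not repair the planning statement.

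**Conclusion.** The point holds for one of the two primary measures. ACT/cACT has no power calculation, and the 0.87 describes an instrument on which the plan draws no conclusion. The assurance of adequate power from two calculations holds at most for activity-limitation days, and only if an SD near 2.05 was used.

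At the plan's own 0.2, power for ACT/cACT with about 95 per arm is about 0.28 on the standardised reading. On the raw-point reading it is 0.28 down to 0.06, the lower end being barely above the 0.05 significance level. These figures assume that the 15% attrition stated for days applies equally to ACT/cACT, a t-test at the full two-sided 0.05, and, for raw points, the assumed SDs. The sample size itself is not invalidated.

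**What to change.** In Section 12.0:

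- State that the 0.87 applies to the ACQ, which is not a primary measure. Give the SD used, and note that at about 95 completers per arm the figure is about 0.85 if that SD was 1.14.
- Limit the adequate-power claim to activity-limitation days.
- Add the ACT/cACT difference detectable with 80% power at about 95 per arm: about 0.41 SD, or about 1.2, 1.6 and 2.0 points for assumed SDs of 3, 4 and 5. Give the SD chosen and its source.
- Reconcile that difference with the 0.2 threshold in Section 9.0, stating the threshold's unit and source.

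Making the ACQ primary in place of ACT/cACT is not the preferred remedy. It would change the hypothesis and the decision rule, and Section 12.0 itself says ACQ variability data for this population are lacking. The visit columns of the outcome table are also not legible in the text available, so ACQ collection at 12 months could not be confirmed there.

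The cost is wording only, with no added data or participants. The downside is that the stated power case becomes less favourable.

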13.0 Regulatory Requirements

13.1 Informed Consent

Written informed consent will be obtained by UIC RS from caregivers in the home before randomization. Before signing the consent, the RS will review the entire document and study protocol. They will answer all questions and ensure the caregiver understands the protocol and consent document. The RS will be bilingual in English and Spanish and all documents will be available in both languages. The protocol for informed consent for Spanish-speakers is the same therefore as for English-speakers.

Assent will be obtained from all children capable of reading and understanding the written assent document. The RS will explain the study protocol using the assent document to ensure the child understands what the document says and what the protocol entails. The caregiver will be present during this process.

The RS will complete human subjects training using the online Citi course at UIC. They will practice obtaining informed consent with volunteers/study staff under the observation of the project manager and/or investigators unless mastery of the process is confirmed.

Signed informed consent/assent documents will be stored in locked cabinets in the Institute for Health Research and Policy. The RS, the project manager, and the PI will have access to the documents.

13.2 Subject Confidentiality

Details for study access, data storage, and data release are described in Sections 8.0, 11.3, and 11.5. These procedures will ensure subject confidentiality will be maintained. No Certificates of Confidentiality will be required.

